5.4.3.2 Management and Dose Modification Guidelines for Rash

Rash is a frequent AE observed in patient receiving trametinib, dabrafenib, or the combination of both agents. HCQ can also cause a rash.

Table 6: Management and Dose Modification Guidelines for Rash

Management and Dose Modification Guidelines for Rash

Supportive care:

Prevention:

 • Avoid unnecessary exposure to sunlight • Apply broad-spectrum sunscreen (containing titanium dioxide or zinc oxide) with a skin protection factor (SPF) ≥ 15 at least twice daily. • Use thick, alcohol-free emollient cream (e.g., glycerine and cetomacrogol cream) on dry areas of the body at least twice daily. • Topical steroids and antibiotics should be applied at least twice daily starting on Day 1 of study treatment, to body areas such as face, chest, and upper back. • Use mild-strength topical steroid (hydrocortisone 1% cream) or topical antibiotic (e.g., clindamycin) or oral antibiotics (e.g., doxycycline 100 mg BID, minocycline 100 mg BID)

Symptom management:

 • Pruritic lesions: cool compresses and oral antihistamine therapies • Fissuring lesions: Monsel's solution, silver nitrate, or zinc oxide cream • Desquamation: thick emollients and mild soap • Paronychia: antiseptic bath, local potent corticosteroids in addition to oral antibiotics; if no improvement, consult dermatologist or surgeon • Infected lesions: appropriate bacterial/fungal culture-driven systemic or topical antibiotics

Notes:

 • Rash prophylaxis is recommended for the first 6 weeks of study treatment • Subjects who develop rash/skin toxicities should be seen by a qualified physician and should receive evaluation for symptomatic/supportive care management

CTCAE Grade	Adverse Event Management	Action and Dose Modification
Grade 1	
 Initiate prophylactic and symptomatic treatment measures Use moderate strength topical steroid.² Reassess after 2 weeks. 	
 Continue HCQ/placebo, dabrafenib and trametinib If rash does not recover to baseline within 2 weeks despite best supportive care, reduce HCQ/placebo by one dose level.²
Grade 2	
 Initiate prophylactic and symptomatic treatment measures. Use moderate strength topical steroid.¹ Reassess after 2 weeks. 	
 Continue dabrafenib and trametinib at the same dose, but reduce HCQ/placebo by one dose level. If rash recovers to ≤ grade 1 within 2 weeks, increase HCQ/placebo dose to previous dose level. If no recovery to ≤ grade 1 within 2 weeks, interrupt HCQ/placebo until recovery to ≤ grade 1. Restart study treatment with HCQ/placebo at reduced dose level.² If no improvement in rash then reduce dabrafenib and trametinib by one dose level and restart the HCQ/placebo at reduced level.
Grade ≥ 3	
 Use moderate strength topical steroids PLUS oral methylprednisolone dose pack.¹ Consult dermatologist. 	
 Interrupt HCQ/placebo, dabrafenib and trametenib until rash recovers to ≤ grade 1. Restart with all three study agents reduced by one dose level If no recovery to ≤ grade 2 within 2 weeks, permanently discontinue study treatment.

1. Moderate-strength topical steroids: Hydrocortisone 2.5% cream or fluticasone propionate concentration 0.05% cream.
2. Study treatment may be escalated to previous dose level if no rash is evident 4 weeks after restarting study treatment.

5.4.3.3 Management and Dose Modification Guidelines for Renal Insufficiency

Cases of renal insufficiency have occurred in patients receiving dabrafenib and the combination of dabrafenib and trametinib. Prior to start of study treatment, concomitant medications should be reviewed for the potential risk of inducing nephrotoxicity and concomitant medications should be modified if clinically possible.

Table 7: Management and Dose Modification Guidelines for Renal Insufficiency

Serum Creatinine Level	Adverse Event Management	Action and Dose Modification
Serum creatinine increase > 0.2 mg/dL (18 umol/L) but ≤ 0.5 mg/dL (44 umol/L) above baseline	
 Recheck serum creatinine within 1 week Serum creatinine increase > 1 week: contact Study chair. If elevation persists beyond 4 weeks, recommend evaluation (consider renal biopsy) for etiology; consider nephrology consultation. 	Continue HCQ/placebo, dabrafenib and trametinib at the same dose level

Serum Creatinine Level	Adverse Event Management	Action and Dose Modification
	
 If pyrexia is present, treat pyrexia as per guidelines^a 	
Serum creatinine increase > 0.5 mg/dL (44 umol/L) above baseline or serum creatinine > 2 mg/dL (> 177 umol/L)	
 Monitor serum creatinine \geq 2-times per week Hospitalization may be necessary if serum creatinine cannot be monitored frequently If pyrexia is present, treat pyrexia per guidelines^a Consult nephrologist if clinically indicated Perform renal biopsy if clinically indicated, for example: 
 Renal insufficiency persists despite volume repletion Patient has new rash or signs of hypersensitivity (such as elevated eosinophil count) 	Interrupt HCQ/placebo, dabrafenib and trametinib 
 until serum creatinine recovers to baseline Restart with HCQ, dabrafenib and trametinib^b

a. NSAIDs can induce renal insufficiency, especially in patients with dehydration; encourage oral fluids or consider intravenous fluids as clinically indicated. See guidelines for pyrexia Section [5.4.3.1](#).

b. Investigator may restart at either the same or a reduced dose level of dabrafenib. Escalation of study treatment to previous dose level is allowed if another episode of renal insufficiency does not occur after 4 weeks of dose reduction. Study treatment may not be restarted if there is evidence of thrombotic microangiopathy.

5.4.3.4 Management and Dose Modification Guidelines for Hepatic Insufficiency

Cases of hepatic insufficiency have occurred in patient receiving dabrafenib and the combination of dabrafenib and trametinib. Prior to start of study treatment, concomitant medications should be reviewed for the potential risk of inducing hepatic toxicity and concomitant medications should be modified if clinically possible.

Table 8: Management and Dose Modification Guidelines for Hepatic Toxicity

Criteria –		Actions	Follow Up Assessments
ALT-absolute	ALT \geq 5xULN	Immediately discontinue dabrafenib, trametinib and HCQ/placebo	Viral hepatitis serology
ALT Increase	ALT \geq 3xULN persists for \geq 4 weeks	Report the event in CTEP-AERS within 7 calendar days.	Blood sample for pharmacokinetic (PK) analysis, obtained within 48 hours after last dose.
Bilirubin	ALT \geq 3xULN and bilirubin \geq 2xULN ($>$ 35% direct bilirubin)	Perform liver event follow up assessments.	Serum creatine phosphokinase (CPK) and lactate dehydrogenase (LDH). Fractionate bilirubin, if total bilirubin \geq 2xULN
INR	ALT \geq 3xULN and INR $>$ 1.5, if INR measured	Monitor the patient until liver chemistries resolve, stabilize, or return to within baseline (see MONITORING below). Do not restart/rechallenge	Obtain complete blood count with differential to assess

Criteria –		Actions	Follow Up Assessments
Cannot Monitor	ALT \geq 3xULN and cannot be monitored weekly for 4 weeks	
patient with study treatment
 
If restart/rechallenge not allowed per protocol or not granted, permanently discontinue study treatment and may continue patient in the study for any protocol specified follow up assessments.
 
MONITORING:
 
For bilirubin or INR criteria:
 
Repeat liver chemistries (include ALT, AST, alkaline phosphatase, bilirubin) and perform liver event follow up assessments within 24 hrs.
 
A specialist or hepatology consultation is recommended.
 
Monitor patient twice weekly until liver chemistries resolve, stabilize or return to within baseline.
 
For All other criteria:
 
Repeat liver chemistries (include ALT, AST, alkaline phosphatase, bilirubin) and perform liver event follow up assessments within 24-72 hrs
 
Monitor patient weekly until liver chemistries resolve, stabilize or return to within baseline
	
eosinophilia
 
Record the appearance or worsening of clinical symptoms of liver injury, or hypersensitivity, on the AE report form.
 
Record use of concomitant medications on the concomitant medications report form including acetaminophen, herbal remedies, other over the counter medications.
 
Record alcohol use on the liver event alcohol intake case report form.
 
For bilirubin or INR criteria:
 
Anti-nuclear antibody, anti-smooth muscle antibody, Type 1 anti-liver kidney microsomal antibodies, and quantitative total immunoglobulin G (IgG or gamma globulins).
 
Serum acetaminophen adduct HPLC assay (quantifies potential acetaminophen contribution to liver injury in patients with definite or likely acetaminophen use in the preceding week).
 
Only in those with underlying chronic hepatitis B at study entry (identified by positive hepatitis B surface antigen): quantitative hepatitis B DNA and hepatitis delta antibody.
 
Liver imaging (ultrasound, magnetic resonance, or computerized tomography) and /or liver biopsy to evaluate liver disease: complete Liver Imaging and/or Liver Biopsy eCRF forms.

5.4.3.5 Management and Dose Modification Guidelines for Pneumonitis

Pneumonitis has been observed in patient receiving trametinib. To reduce the risk of pneumonitis, patient will be monitored closely for symptoms, evaluated with imaging and functional tests.

Table 9: Management and Dose Modification Guidelines for Pneumonitis of Trametinib only

CTCAE Grade	Adverse Event Management	Action and Dose Modification
Grade 1	
 • CT scan (high-resolution with lung windows) recommended • Clinical evaluation and laboratory work-up for infection • Monitoring of oxygenation via pulse-oximetry recommended • Consultation with pulmonologist recommended 	
 • Continue trametinib at current dose
Grade 2	
 • CT scan (high-resolution with lung windows) • Clinical evaluation and laboratory work-up for infection • Consult pulmonologist • Pulmonary function tests -if < normal, repeat every 8 weeks until \geq normal • Bronchoscopy with biopsy and/or bronchioalveolar lavage (BAL) recommended • Symptomatic therapy including corticosteroids if clinically indicated 	
 • Interrupt trametinib until recovery to grade ≤ 1 • Restart treatment with trametinib reduced by one dose level
Grade 3	
 • CT scan (high-resolution with lung windows) • Clinical evaluation and laboratory work-up for infection • Consult pulmonologist • Pulmonary function tests-if < normal, repeat every 8 weeks until \geq normal • Bronchoscopy with biopsy and/or BAL if possible • Symptomatic therapy including corticosteroids as clinically indicated 	
 • Interrupt trametinib until recovery to grade ≤ 1, then restart at reduced dose. • If no recovery to grade ≤ 1 within 4 weeks, permanently discontinue trametinib
Grade 4	
 • Same as grade 3 	
 • Permanently discontinue trametinib • Unblinding may be allowed to improve medical care. See Section 4.5

5.4.3.6 Management and Dose Modification Guidelines for Reduced Left ventricular ejection fraction (LVEF)

Decreases in left ventricular ejection fraction have been seen with the use of trametinib with an incidence of 9% with the combination of trametinib and dabrafenib compared to 0% with dabrafenib alone. Therefore, transthoracic echo must be performed at baseline and repeated every 3 months while on study or as clinically indicated. More frequent evaluation is warranted if there are signs or symptoms suggestive of clinical CHF. The same procedure (either ECHO or MUGA, although ECHO

is preferred) should be performed at baseline and at follow-up visit(s).

Table 10: Management and Dose Modification Guidelines of Trametinib for LVEF Decrease

Clinic	LVEF-drop (%) or CTCAE grade	Action and Dose Modification
Asymptomatic	Absolute decrease of > 10% in LVEF compared to baseline and ejection fraction below the institution's LLN	
Interrupt trametinib and repeat ECHO within 2 weeks^{a,b}
 
If the LVEF recovers within 4 weeks (defined as LVEF \geqLLN and absolute decrease \leq10% compared to baseline) then restart at a reduced dose level of trametinib.
 
 Repeat ECHO at 2, 4, 8 and 12 weeks after re-start; continue in intervals of 12 weeks thereafter 
If LVEF does not recover within 4 weeks
 
 Consult with cardiologist Permanently discontinue trametinib Report as SAE Repeat ECHO after 2, 4, 8, 12, and 16 weeks or until resolution
Symptomatic ^b	Grade 3: resting LVEF 39-20% or >20% absolute reduction from baseline	
Permanently discontinue trametinib
 
Report as SAE
 
Interrupt dabrafenib.^c
 
Consult with cardiologist
 
Repeat ECHO after 2, 4, 8, 12, and 16 weeks or until resolution
 
Grade 4 toxicity will trigger unblinding per Section 4.5

	Grade 4: resting LVEF < 20%	

- If ECHO does not show LVEF recovery after 2 weeks, repeat ECHO 2 weeks later.
- Symptoms may include: dyspnea, orthopnea, and other signs and symptoms of pulmonary congestion and edema.
- Once LVEF recovers, including resolution of symptoms, restart of dabrafenib monotherapy will be at the discretion of the study investigator.

5.4.3.7 Management and Dose Modification Guidelines for QTc prolongation

Both dabrafenib and trametinib have been shown to prolong the QTc interval. However, to date, there are no clinical adverse event reports attributable to QTc interval prolongation or manifest cardiac arrhythmias. However, the following recommendations have been developed to minimize the risk of ventricular tachyarrhythmias in patients with metastatic melanoma treated with this regimen:

- Avoid combination with other drugs with potential to lead to prolongation of QTc interval, if possible.
- ECG should be monitored at baseline, and each cycle (monthly) thereafter.

- Monitor ECG weekly until the QTc interval decreases to < 500 msec, or a cardiologist provides documentation that it is safe to resume therapy before reinstituting therapy at a reduced dose.

Table 11: Management and Dose Modification Guidelines for QTcB-Prolongation

(QT interval on electrocardiogram corrected using the Bazett's formula) QTc-Prolongation ^a	Action and Dose Modification
QTcB ≥501 msec (milliseconds)	
Interrupt all three study agents until QTcB prolongation resolves to grade 1 or baseline
 
Test serum potassium, calcium, phosphorus and magnesium. If abnormal correct per routine clinical practice to within normal limits.
 
Review concomitant medication usage for agents that prolong QTc.
 
If event resolves, restart study treatment at current dose level^b
 
If event does not resolve, discuss with a cardiologist, if deemed clinically significant then discontinue study treatment
 
If event recurs, discuss with a cardiologist, if deemed clinically significant then permanently discontinue study treatments

a Based on average QTc value of triplicate ECGs. For example, if an ECG demonstrates a prolonged QT interval, obtain two or more ECGs over a brief period, and then use the averaged QTc values of the three ECGs to determine if study treatments should be interrupted or discontinued.

b If the QTc prolongation resolves to grade 1 or baseline, the patient may resume study treatment.

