5.4.1.2 Dose Level Reduction Tables

Table 1: Dabrafenib Dose Level Reductions

Dose Level	Dose/Schedule
Starting Dose	150 mg twice daily
First Reduction	100 mg twice daily
Second Reduction	75 mg twice daily
Third Reduction	50 mg twice daily
If unable to tolerate 50 mg twice daily	Discontinue dabrafenib

Trametinib Dose Reductions

Table 2: Trametinib Dose Reductions

Dose Level	Dose/Schedule
Starting Dose	2 mg twice daily
First Reduction	1.5 mg twice daily
Second Reduction	1.0 mg twice daily
Third Reduction	0.5 mg twice daily
If unable to tolerate 0.5 mg once daily	Discontinue trametinib

Hydroxychloroquine/Placebo Dose Reductions

Table 3: HCQ/placebo Dose Reductions

Dose Level	Dose/Schedule
Starting Dose	600 mg twice daily
First Reduction	600 mg once daily in the morning and

Dose Level	Dose/Schedule
	400 mg once daily in the evening
Second Reduction	400 mg twice daily
Third Reduction	A third dose reduction to 400 mg once a day (qd) may be pursued in patients deemed to be deriving clinical benefit at the discretion of the treating physician.

For any AE with a grade ≥ 3 , HCQ/placebo dose will be held until the toxicity resolves to \leq grade 1 before restarting, after which HCQ/placebo may be restarted at a reduced dose as described in table 3.

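### Section 5.4.3.7 contradicts itself on the dose, and on the condition, for restarting treatment after QTc prolongation

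*Combined protocol and SAP*

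**What the plan says.** Section 5.4.3.7 of the protocol deals with QTc prolongation in three bullets followed by Table 11.

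- **Third bullet.** "Monitor ECG weekly until the QTc interval decreases to < 500 msec", or until a cardiologist has documented that it is "safe to resume therapy before reinstituting therapy at a reduced dose". It refers only to therapy. It does not say which drug or drugs are reduced, or by how many levels.
- **Table 11.** The single row is triggered at QTcB of 501 msec or more. The action is "Interrupt all three study agents until QTcB prolongation resolves to grade 1 or baseline", and then "If event resolves, restart study treatment at current dose level". If the event does not resolve, or recurs, the case goes to a cardiologist, and treatment is discontinued if the event is judged clinically significant.
- **Table 11, footnote b.** "If the QTc prolongation resolves to grade 1 or baseline, the patient may resume study treatment". No dose is given.

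Elsewhere, the general text under Table 3 in Section 5.4.1.2 holds HCQ/placebo for any adverse event of grade 3 or higher until grade 1 or less, "after which HCQ/placebo may be restarted at a reduced dose as described in table 3".

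**The concern.** The bullet and the table cover the same event in the same section, yet one gives a reduced dose on restart and the other the current dose. Their conditions for restarting differ as well: below 500 msec or a cardiologist's clearance in the bullet, grade 1 or baseline in the table.

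The section's stated aim is to limit the risk of ventricular tachyarrhythmia. It says that dabrafenib and trametinib prolong QTc, and Sections 8.3.8 and 8.3.10 say the same of HCQ. Because HCQ/placebo is double-blind, a site cannot tell whether HCQ is contributing and has to rely on the written rule. If sites follow different lines, like patients will be rechallenged at different doses and at different points in recovery. That matters for safety and for uniform conduct, in both arms.

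**Working it through.** The plan states no figure here to reproduce. The check is a comparison of the two texts, followed by a rough size.

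**1. The two rules side by side**

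| Situation after QTcB of 501 msec or more | Third bullet | Table 11 |
|---|---|---|
| QTc back to baseline, below 500 msec | restart, reduced dose | restart, current dose level |
| QTc below 500 msec, not yet grade 1 or baseline | restart, reduced dose | stay interrupted |
| QTc not below 500 msec, cardiologist documents safety | restart, reduced dose | unresolved: discuss with cardiologist, discontinue if clinically significant; otherwise silent |

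The first row is a direct conflict of dose. It is not a corner case: eligibility criterion 3.1.18.2 excludes a Bazett-corrected QT of 480 msec or more, so an eligible patient who returns to baseline is also below 500 msec. The second row is a conflict of restart condition. In the third row the two texts might complement each other.

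**2. Search for a tie-breaker**

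- Footnote b permits resumption but is silent on dose.
- The Table 4 caption lets toxicity-specific sections depart from the general guidance. Both lines are in the same specific section, so this does not choose between them.
- Section 5.4.1.4 allows re-escalation after resolution to grade 1 or less. That does not set the dose at restart.
- The text under Table 3 is permissive and covers HCQ/placebo only. It cannot settle dabrafenib or trametinib.
- Other tables show how the protocol words such rules when they are explicit. Table 7, footnote b, gives the investigator a choice between the same and a reduced dabrafenib dose. Table 12, Scenario C, names three treatments and one level. The QTc bullet does neither.

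No tie-breaker was found.

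**3. How many patients**

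The adverse event table in Section 1.1.4 lists one grade 3 QTc event, printed as 4%. No denominator is printed; 1/0.04 = 25 is implied. Sections 1.1 and 1.1.2 give 38 patients evaluable for toxicity. With 84/2 = 42 patients in Arm A:

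- 1/25 = 4.0% (exact 95% CI 0.1% to 20.4%); × 42 = 1.7 patients (0.04 to 8.5)
- 1/38 = 2.6% (exact 95% CI 0.07% to 13.8%); × 42 = 1.1 patients (0.03 to 5.8)

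Both lines take grade 3 as a stand-in for QTcB of 501 msec or more. The documents do not define the QTc grades, so that is an assumption. No count is offered for Arm B, because the comparator rate for dabrafenib plus trametinib is shown as not reported.

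**4. How large a dose difference**

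The bullet gives no number of levels. If it means one level down from the starting doses, with trametinib once daily as in Section 5.1, then:

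- dabrafenib 300 to 200 mg/day: 1 − 200/300 = 33%
- trametinib 2 to 1.5 mg/day: 1 − 1.5/2 = 25%
- HCQ/placebo 1200 to 1000 mg/day: 1 − 1000/1200 = 17%

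The HCQ/placebo line applies only if therapy in the bullet includes it.

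**The case against.** The best defence is that the lines divide the cases between them. Table 11 sends unresolved events to a cardiologist and discontinues only those judged clinically significant. Some unresolved events could therefore continue, and the table gives them no dose. The bullet's cardiologist route, with its reduced dose, could fill that gap, leaving the current dose for full resolution. So it would be too strong to say that the two texts can never be read as successive steps. But the protocol does not state this division. The bullet also names QTc below 500 msec as a route of its own, and a patient back at baseline still satisfies both lines. The reading narrows the conflict without removing it.

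Three stronger inferences are tempting, and the documents do not support them:

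- **That all three drugs, HCQ included, will be restarted at different doses.** Table 11 does cover all three agents, but the bullet says only therapy, and the section opens by naming dabrafenib and trametinib alone. A difference in HCQ/placebo dose is one possible reading.
- **That the problem falls mainly on Arm A and so distorts the comparison.** The stated QT effect of HCQ makes more events in Arm A plausible. No comparative rate is given, and both arms receive two drugs said to prolong QTc.
- **That the text under Table 3 is a further contradiction.** It says that a reduced restart may be used, and for HCQ/placebo only. It needs checking against whatever rule is chosen, but it does not oppose Table 11 as the bullet does.

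**Conclusion.** The section is inconsistent as written. For an eligible patient who recovers to baseline after QTcB of 501 msec or more, the bullet and Table 11 give different restart doses, and no provision says which governs. The restart conditions differ too. That much follows from the text alone and needs no numerical assumption.

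The likely reach is small: about 1 to 2 Arm A patients, with exact limits running from near 0 to about 9 on the less favourable denominator. This rests on a single event, on an uncertain denominator (25 or 38), on the BAMM rate carrying over to this trial, and on equating grade 3 with the trigger. The percentage dose differences depend further on a one-level reduction from the starting doses.

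The weight of the point is safety and consistent conduct in both arms. No effect on the primary comparison of one-year PFS, its power or its type I error has been shown.

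**What to change.** The sponsor's clinical team should reconcile the third bullet of Section 5.4.3.7 with Table 11, covering both the restart condition and the restart dose. The result should be one rule that names the drug or drugs it covers and, if it involves a reduction, the number of levels. It should also say what applies to an unresolved event that the cardiologist does not judge clinically significant. The conflicting wording should be deleted, and the general HCQ/placebo text under Table 3 checked for agreement. Which rule is right is a clinical decision on which this review takes no position.

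The cost is a short wording amendment touching the bullet, Table 11 and possibly the text under Table 3. It needs no new procedures or data and leaves the sample size and analysis unchanged.
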